This technological revolution has progressively affected the health world. An increasing number of medical APP have been designed in the last years, few directly managed from health care providers from public or private centers. ThemHealth (Mobile Health) APP could led to a simpler, real-time connection between patients and health care professionals alongside with a bidirectional data flow and a steadily monitorization of patients' evolution that could obtain a better preoperative follow-up without increasing the costs [24-26].

The present randomized clinical trial aims to prove the safety and efficacy of an interactive mobile application (Care4Today®) to obtain sufficient weight loss and empower patients with morbid obesity before being submitted to a gastric by-pass.

HYPOTHESIS:

Main hypothesis: The preoperative use of the Care4Today (C4T) application in addition to standard protocol, in patients with a grade II-III obesity (BMI between 35 and 50 Kg/m²) achieves greater preoperative weight loss than standard protocols.

Secondary Hypothesis: Use of the Care4Today (C4T) application in the preoperative setting achieves:

- less intra- and post-operative complications at 30 and 90 days;
- less technical complexity and duration of surgery;
- better patients' information and satisfaction;
- better medical team coordination and satisfaction;
- better weight loss outcomes at mid-term (1, 3 and 5 years).

AIMS:

Main goal: To compare patients' preoperative weight loss after using the C4T APP in addition to standard protocol versus the standard preoperative protocol.

Secondary goals:

1. Compare patients' information / satisfaction using the APP vs. standard protocol.
2. Compare complications in the immediate postoperative period (30- and 90-days post-intervention) after the preoperative use of APP vs. standard protocol.
3. Compare medical team coordination / satisfaction using the APP vs. standard protocol.
4. Compare patients' weight loss 3 months after surgery using the APP vs. standard protocol.

STUDY DESIGN: Randomized Clinical Trial to assess the safety and efficacy of a mobile application to monitor patients undergoing bariatric surgery.

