All patients will receive the standard preoperative protocol that consist in optimization of associated complications with an active management of obesity-related comorbidities, optimization of preoperative weight loss through a hypocaloric diet carried out during the 10-15 days prior to surgery and an informative and educational group session prior to surgery (EDUBAR). The C4T APP will be provided four months before surgery to all the patients randomized in the APP group. All the contents in the APP have been properly selected and modified by the multidisciplinary team (endocrinologist, pneumologist, anaesthesiologist, psychiatrist, nutritionist, nursery). Specifically, the APP contents include informative articles covering the nutritional, behavioral, and surgical fields, exercises, interactive charts, instructional videos, surgical animations, checklists, and frequently asked questions. The format of the APP will lead the patient through a virtual journey in the world of bariatric surgery, allowing to understand all the basic information about the preoperative period, the surgery and hospitalization and the postoperative follow-up. The use of the APP will influence preoperative weight loss through all the information provided, designed in an intuitive way so that the patient progresses in their level of knowledge and can assess through a checklist if they are doing the correct training. It will allow patients to set specific goals and assess their scope. Making patients aware of the importance of preoperative weight loss through training will be the key to obtaining correct adherence to the program and satisfactory preoperative weight loss. No patient data will be saved on the APP.

To assess the impact of the APP, in addition to standard protocol, in the pre- and postoperative period, we will compare:

- preoperative total weight loss percentage
- level of patient information
- level of patient satisfaction
- level of medical team satisfaction
- 30th and 90th days postoperative morbidity and mortality
- percentage of weight loss 3 months after surgery

CHRONOGRAM:

OBSERVATION PERIOD

Recruitment period of the study is expected to be 18 months, with additional 6 months to perform surgeries and follow-up. All information's will be obtained using the application flow of data alongside with presential meeting with surgeons, endocrinologists, nutritionists.

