S. All the contents in the APP have been properly selected and modified by the multidisciplinary team. The day of surgery all the data about weight loss, patient and medical team satisfaction will be collected. Then, patients will be followed in observation of our standard postoperative protocol to assess the 30th and 90th postoperative morbidity and mortality alongside with weight loss evolution. The PhD student has been directly involved in the APP design and contents creation. He will perform the preoperative presential meeting to provide and explain the APP functioning to the patients in the APP group. Furthermore, he will collect the data on the day of surgery, during surgery and will be directly involved in postoperative follow-up of all patients.

STUDY POPULATION:

Inclusion criteria:

- Patients older than 18 and younger than 65 years who meet criteria to undergo bariatric surgery
- BMI between 35 and 50 kg/m² and indication of one-time surgery
- Signing the informed consent of the study
- Patient suitable for laparoscopic surgery
- Patient who demonstrates accessibility to a smartphone and basic digital competence (Appendix 1).

Exclusion criteria:

- Previous bariatric surgery
- Two-step surgery
- Patient without resources to access the use of a Smartphone or without basic digital competence
- Contraindication for surgery
- Other surgical procedures associated with the same intervention

Retirement criteria:

- None

EXPERIMENTAL TREATMENT: Use of a mobile application to accompany and empower patients in the preoperative period.

EVALUATION CRITERIA:

Main criteria (for the main goal): Preoperative percentage of excess weight lost (%EWL), considering ideal BMI = 25, will be recorded.

Following the follow-up protocol in General Surgery Outpatient Consultations, patients' weight will be measured 4 months before surgery and on the same day of surgery; then at 3, 6 and 12 months, and then every year up to 5 years of follow-up to calculate BMI and percentage of overweight lost, percentage of BMI lost, total weight and BMI lost.

Secondary criteria (for secondary goals):

1. Patients' information and satisfaction using the APP vs. standard protocol will be evaluated using approved questionnaire (appendix 2, appendix 3);

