2. Morbidity and mortality: morbidity and mortality will be evaluated using the prospective database of the Bariatric Surgery Unit and the electronic medical record of each patient. All perioperative aspects related to the surgery will be reviewed. Complications will be recorded according to the Clavien-Dindo classification.
3. Metabolic comorbidities: Comorbidities related to metabolic syndrome and morbid obesity will be recorded to study their evolution up to 5 years after the intervention: DM2, hypertension, DL and OSAS.
4. Medical team coordination and satisfaction using the APP vs. standard protocol will be evaluated during multidisciplinary committee.
5. Patients weight loss 3 months after surgery will be evaluated using the prospective database of the Bariatric Surgery Unit and the electronic medical record of each patient.
6. Nutritional and metabolic deficiencies: The analytical studies performed each year on these patients will be evaluated to detect possible deficiencies: protein, iron, phosphocalcic, fat-soluble vitamins and trace elements.

STUDY DURATION:

The study is expected to begin in October 2022

Patient recruitment period is expected from October 2022 to March 2024.

Preoperative follow-up will be completed the day of surgery.

Mid-term follow-up (2 years) will be completed in March 2026.

Long-term follow-up (5 years) will be completed in March 2029.

SAMPLE SIZE:

The sample size was calculated in 142 patients divided into two groups of 71 patients each. It was calculated by comparing a hypothetical reduction of ≥ 5 kg in 55% of patients in the C4T group vs in 39% of patients in the control group [27] with a possible loss of 16% of patients, a confidence level of 95%, and statistical power of 80%.

STATISTICAL ANALYSIS:

Continuous variables will be expressed as mean \pm standard deviation or median (interquartile range) as appropriate. Differences between both techniques will be evaluated using a parametric test (χ^2 for categoric variables and t test for continuous variables). We'll use the IBM-SPSS Statistics Version 20 computer software to analyse all the statistics. A p value < 0.05 will be considered statistically significant.

PERSONAL DATA PROTECTION / CONFIDENTIALITY / ETHICAL ASPECTS:

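### Weight loss 3 months after surgery has no stated reference weight, and counting it from the day of surgery would understate the APP's total effect and could reverse its sign

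*Combined protocol and SAP*

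**What the plan says.** All places are in section 1 (RESUME) of the combined protocol and SAP.

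- AIMS, secondary goal 4: "Compare patients' weight loss 3 months after surgery using the APP vs. standard protocol". No reference weight is given.
- STUDY DESIGN, list of comparisons: "percentage of weight loss 3 months after surgery". There is no formula. Preoperative weight loss is a separate item in the same list.
- EVALUATION CRITERIA, secondary criterion 5: "Patients weight loss 3 months after surgery will be evaluated using the prospective database of the Bariatric Surgery Unit" and the medical record. This names the data source only.
- EVALUATION CRITERIA, main criterion: "weight will be measured 4 months before surgery and on the same day of surgery; then at 3, 6 and 12 months", then yearly to 5 years, "to calculate BMI and percentage of overweight lost, percentage of BMI lost, total weight and BMI lost". No denominator is named. The %EWL definition with ideal BMI 25 is given for the preoperative outcome only.
- STUDY DESIGN: the APP is handed out four months before surgery and is expected to influence preoperative weight loss. HYPOTHESIS makes greater preoperative loss the main hypothesis and adds better weight outcomes at 1, 3 and 5 years.
- STATISTICAL ANALYSIS: continuous variables are compared by t test, and no covariate is mentioned.

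**The concern.** Two preoperative weights are scheduled, and either could serve as the starting point for loss at month 3. They are not interchangeable. The weight 4 months before surgery belongs to the period before the APP can act. The day-of-surgery weight comes after APP use, and if the main hypothesis is right it will be lower in the APP arm. Loss counted from there leaves out what the APP achieved before surgery and gives the APP arm a lower starting point.

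Two analysts could therefore follow the plan faithfully and report contrasts of different size, and in some circumstances of opposite sign. The weights out to 5 years have the same undefined reference. The choice should be made before results are seen, particularly as the person who helped design the APP also collects the day-of-surgery data and takes part in follow-up.

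**Working it through.** The plan gives no figure for this comparison, so there is none to reproduce. It also gives no weights or standard deviations. **Every weight below is an assumption**; only the measurement times, the ideal BMI of 25 and the 71 patients per group come from the plan.

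**Notation.** B is the weight 4 months before surgery, equal in both arms. Sc and Sa are the day-of-surgery weights (control, APP), and Wc and Wa the month-3 weights. The APP's extra preoperative loss is e = Sc - Sa, and r is the share of e still present at month 3, so Wa = Wc - r·e.

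**Contrasts (APP minus control) on percentage of total weight.**
- From the pre-APP weight: (Wc - Wa)/B = r·e/B. This is never negative when the APP arm is as light or lighter at month 3.
- From the day of surgery: Wc/Sc - Wa/Sa = e·(r - Wc/Sc)/Sa. This is negative whenever r < Wc/Sc, that is, whenever r is below 1 minus the control arm's fractional loss since surgery.

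**Example 1.** B = 120 kg; preoperative loss 6 kg (APP) and 4 kg (control), so Sa = 114, Sc = 116 and e = 2.

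| Month-3 weight, APP / control | From pre-APP weight | From day of surgery |
|---|---|---|
| 95 / 95 kg (r = 0) | 25/120 = 20.8% in both; 0 | 19/114 = 16.7% vs 21/116 = 18.1%; -1.4 points |
| 94 / 95 kg (r = 0.5) | 26/120 = 21.7% vs 20.8%; +0.8 points | 20/114 = 17.5% vs 18.1%; -0.6 points |

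The break-even is r = 95/116 = 82%.

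**Example 2.** B = 120 kg; preoperative loss 7 kg (APP) and 4 kg (control); control loses 25 kg after surgery, so Wc = 91.

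| Share retained | From pre-APP weight | From day of surgery |
|---|---|---|
| 0 | 29/120 = 24.2% in both; 0 | 22/113 = 19.5% vs 25/116 = 21.6%; -2.1 points |
| 0.5 | 30.5/120 = 25.4% vs 24.2%; +1.25 points | 23.5/113 = 20.8% vs 21.6%; -0.8 points |
| 1 | 32/120 = 26.7% vs 24.2%; +2.5 points | 25/113 = 22.1% vs 21.6%; +0.6 points |

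The break-even is 91/116 = 78%.

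**Range of the break-even.** With 4 kg control loss before surgery: a 110 kg start and 25 kg lost after surgery gives 1 - 25/106 = 76%; a 130 kg start and 20 kg lost gives 1 - 20/126 = 84%.

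**On %EWL.** Subtract the ideal weight I from each denominator; the break-even becomes 1 minus the control arm's %EWL since surgery. At an assumed starting BMI of 43, I = 120 × 25/43 = 69.8 kg.
- Example 2: control 25/46.2 = 54.1%, so break-even is about 46%. With r = 0, both arms show 57.7% from the pre-APP weight, but 50.9% (APP) vs 54.1% from the day of surgery.
- Example 1 at 94 / 95 kg: 20/44.2 = 45.2% vs 21/46.2 = 45.4%, or -0.2 points. At an assumed BMI of 40 (I = 75 kg): 20/39 = 51.3% vs 21/41 = 51.2%, with no reversal.

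**Size against noise.** With 71 per arm, p < 0.05 needs about 1.96 × √(2/71) = 0.33 SD: 1.3 points at an assumed SD of 4, and 2.6 at an SD of 8. The day-of-surgery contrast of -0.6 (unrounded -0.56) would be non-significant at any SD above about 0.56/0.33 = 1.7 points.

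**The case against.** Nothing in the plan says that loss is counted from the day of surgery. A reader might infer it, because preoperative loss and 3-month loss are listed as separate outcomes and one seems to start where the other ends. But the phrase can equally mean total loss assessed at month 3. The weight schedule is a single series starting 4 months before surgery, and the primary outcome must already use that first weight. This stands: the defect is an open choice, not a wrong baseline that has been adopted.

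A reader might also infer that a post-randomisation baseline breaks the randomised comparison. It does not. Nobody is selected or stratified on the day-of-surgery weight; the arms are compared as allocated, and the contrast validly estimates the APP's effect on the interval after surgery. The trouble comes if that is read as the APP's effect on weight overall.

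The reversal is conditional and depends on the metric, and it is shown here for point estimates only. A reader might go further and expect a successful APP to be declared significantly worse. The documents give no variability with which to support that, and contrasts of this size could easily be non-significant.

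Finally, naming the reference weight alone settles the direction problem, and covariate adjustment is a separate improvement. That is fair. Adjustment is proposed because the fix turns the pre-APP weight into the baseline, and an unadjusted t test leaves chance imbalance in it uncorrected.

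**Conclusion.** The point holds as an unresolved definition with consequences. The plan does not fix the reference weight for 3-month loss, and one of the two permitted readings uses a weight that the APP is intended to change. In both examples that reading understates the total effect even when all the extra preoperative loss is kept (+0.6 instead of +2.5 points in example 2). It reverses the sign when the retained share is below about 76-84% on percentage of total weight, for assumed starting weights of 110-130 kg and 20-25 kg lost after surgery. On %EWL at an assumed BMI of 43 the threshold is lower: about 46% in example 2 and, from 1 - 0.454, about 55% in example 1.

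All of these sizes rest on assumed weights. The same formula applies to later visits, but no figures were worked out for them, and 1, 3 and 5 years appear as hypotheses rather than as listed secondary goals. The primary analysis is not affected. The point deserves correction before analysis because the direction of a secondary result can turn on an unstated choice.

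**What to change.** 1. In EVALUATION CRITERIA, define every postoperative weight-loss outcome, from 3 months to 5 years, as loss from the weight measured 4 months before surgery, and name the metric (percentage of total weight or %EWL). State that this weight is taken before APP access: the plan puts both at four months before surgery without giving their order, and it does not give the date of randomisation.
2. In STATISTICAL ANALYSIS, replace the plain t test for these outcomes with ANCOVA using that same weight as covariate. Adjustment alone would not cure an outcome counted from the day of surgery; the reference itself has to be fixed.
3. Report loss since the day of surgery by arm as description only, with no between-arm claim.

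The cost is a few sentences in two sections. Both weights are already scheduled, so no new visit, measurement or patient is needed.

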Appendix 3: Questionnaire to assess patients' satisfaction:

PATIENT SATISFACTION QUESTIONNAIRE – VAMOS PROJECT

	Scarce	Poor	Good	Very good	Excellent
1. Kindness/Courtesy of the medical team.....					
2. Explanations of the medical team about your pathology.....					
3. Interest that the team has shown in clearing up your doubts and concerns.....					
4. Willingness of the medical team to include you in treatment decisions					
5. Information provided by the team on the type of medication.....					
6. Instructions provided by the medical team on follow-up.....					
7. Comprehensibility of the language of the information received.....					
8. Time that the medical team has dedicated to you.....					
9. Your confidence in this medical team.....					
10. Probability that you recommend this medical team to other patients.....	

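### The person who helped create the app and explains it to the app arm appears also to collect the patient satisfaction forms, and no independent return route is described

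*Combined protocol and SAP*

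**What the plan says.** All the role descriptions stand in one paragraph of section 1, in the Chronogram text just before Study population.

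- Timing: "The day of surgery all the data about weight loss, patient and medical team satisfaction will be collected".
- Link to the intervention: "The PhD student has been directly involved in the APP design and contents creation".
- Delivery, to one arm only: "He will perform the preoperative presential meeting to provide and explain the APP functioning to the patients in the APP group".
- Data collection: "he will collect the data on the day of surgery, during surgery and will be directly involved in postoperative follow-up of all patients".

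Secondary goal 1 under Aims is to compare patients' "information / satisfaction using the APP vs. standard protocol". Under Evaluation criteria, the first secondary criterion says that these outcomes "will be evaluated using approved questionnaire (appendix 2, appendix 3". Appendix 3, the "PATIENT SATISFACTION QUESTIONNAIRE", has ten items, each rated on five levels from scarce to excellent. The items concern the medical team: its courtesy, its explanations, the time it gave, the patient's trust in it and whether the patient would recommend it.

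The design, evaluation and analysis text does not mention masking or an independent assessor. Neither appendix says who hands out the form, where it is completed or to whom it is returned.

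**The concern.** A satisfaction rating can depend on who receives it. Here the apparent recipient has a stake in the app and has held a personal meeting with patients in one arm to introduce it. No matching meeting with him is described for control patients. If app patients hand their ratings to him, or complete them in front of him, some may rate more generously than they otherwise would, and control patients would have less reason to do so. The between-arm difference in satisfaction would then partly reflect the way the forms were gathered. At stake is the reading of one subjective secondary outcome, which the protocol lists among its hypotheses and goals.

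**Working it through.** No figure in the plan bears on this point, so the check is a reading of the text in four steps.

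**1. Does he collect satisfaction?** One sentence places patient satisfaction among the data gathered on the day of surgery, in the passive voice and without naming a collector. A later sentence in the same paragraph names the PhD student as collector of that day's data. Read together, they make him the collector of the satisfaction forms. No single sentence says so.

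**2. Does he know the allocation?** Yes, for the app arm. He meets those patients in person to give them the app and explain it.

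**3. Is there a safeguard elsewhere?**

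| Place in the document | What it covers | Does it protect patient satisfaction? |
|---|---|---|
| Evaluation criteria, secondary criterion 1 | Names the questionnaires | No: the instrument is given, not how it is administered |
| Evaluation criteria, morbidity and 3-month weight loss | Unit database and medical record | No: other outcomes |
| Evaluation criteria, team satisfaction | Multidisciplinary committee | No: a different outcome |
| Confidentiality | Database access for study investigators only | No: this is data protection, not masking |
| Appendices 2 and 3 | Text of the forms | No: no rule on completion or return |

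**4. What could the collector change?** The observed difference in mean satisfaction (app minus control) can be written as

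observed = true difference + effect of patients knowing their arm + (collector effect in app arm − collector effect in control arm).

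If patients in both arms are equally reluctant to criticise in front of him, the bracket is zero. It favours the app only if the reluctance is greater in the app arm. The extra meeting makes that plausible, but nothing in the documents shows it. The documents give no scoring rule for Appendix 3, no standard deviation and no expected difference, so neither the sign nor the size of the bracket can be calculated.

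Appendix 2 is less exposed. It is a multiple-choice knowledge test, and patient information is not in the list of data gathered on the day of surgery. Its day of administration is not stated.

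**The case against.** The strongest reply is that the plan is merely silent on procedure. It does not say that the student interviews patients, watches them complete the form or scores it. Appendix 3 is a tick-box form that patients can fill in alone. The phrase on day-of-surgery collection could also be read as meaning perioperative data. In addition, the form rates the medical team rather than the app, and he has contact with patients in both arms. The paragraph begins with a broken fragment in the available text, so nearby words may be missing.

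Much of this stands. It is why his role in collecting satisfaction is stated as an inference and the direction of bias only as plausible. It does not remove the point: the roles in app creation, delivery and data collection are written down for one person, and the route that would separate him from the ratings is not.

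A reader might infer more than the documents support:

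- *The primary outcome is compromised.* The main criterion is "Preoperative percentage of excess weight lost (%EWL), considering ideal BMI = 25, will be recorded", and weight loss is among the day-of-surgery data. But weight is a measured quantity, scheduled under the surgical outpatient follow-up protocol, and nothing says that he weighs the patients. No defect is shown there.
- *Complication grading is affected.* No text says that he grades complications. The named sources are the unit database and the medical record.
- *Team satisfaction is affected in the same way.* It is listed with the day-of-surgery data, but Evaluation criteria assigns it to the multidisciplinary committee, so his part is unclear.
- *The absence of masking is itself the fault.* Patients cannot be masked to an app they use. The avoidable part is the collector's role.

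**Conclusion.** The point holds as a minor one, limited to patient satisfaction. A person who helped create the app and delivers it to one arm is, on the natural reading, also the collector of a subjective rating, with no independent return described. This leaves the satisfaction comparison open to a collector effect. It does not show that the comparison is biased, and neither size nor direction can be estimated from the documents.

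The conclusion rests on two assumptions: that the two Chronogram sentences are meant to be read together, and that no separate procedure for handling the forms exists outside the text available for review. If such a procedure exists, citing it in the protocol would settle the matter.

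**What to change.** Amend the Chronogram paragraph in two respects.

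1. Patients in both arms complete Appendix 3, and Appendix 2 whenever it is given, by themselves. They return it in a closed envelope, without the PhD student present, to existing staff who are not involved in delivering the app.
2. State that the trial is open-label, and report patient satisfaction as an unmasked outcome.

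The first change removes only the part of any bias that runs through the collector. Patients still know their arm, which is why the second is needed. Since the protocol says that the multidisciplinary team selected and modified the app's contents, the practical aim is separation from delivery of the app. The closed envelope matters because the form rates that same team.

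The cost is a few sentences of protocol text and a small reallocation of tasks within the existing team: someone other than the PhD student must hand out and receive the forms. No new form or visit is needed. The documents do not describe staffing, so the sponsor should confirm who can take this on.

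### The main criterion is percent excess weight loss, but the design section compares percent total weight loss and the sample size uses a ≥5 kg responder rate; the three are never reconciled

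*Combined protocol and SAP*

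**What the plan says.** All places are in the combined protocol and SAP, under 1. RESUME.

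- **AIMS, main goal:** "To compare patients' preoperative weight loss after using the C4T APP in addition to standard protocol versus the standard preoperative protocol". No unit or formula is given.
- **STUDY DESIGN, list of comparisons used to assess the app:** the first item is "preoperative total weight loss percentage" (%TWL below).
- **EVALUATION CRITERIA, main criterion for the main goal:** "Preoperative percentage of excess weight lost (%EWL), considering ideal BMI = 25, will be recorded" (%EWL below). The next paragraph says that "patients' weight will be measured 4 months before surgery and on the same day of surgery", with later weighings after surgery, "to calculate BMI and percentage of overweight lost, percentage of BMI lost, total weight and BMI lost".
- **SAMPLE SIZE:** 142 patients, 71 per group, from a "hypothetical reduction of ≥ 5 kg in 55% of patients in the C4T group vs in 39% of patients in the control group", with 16% loss, 95% confidence and 80% power.
- **STATISTICAL ANALYSIS:** χ² for categorical variables, t test for continuous ones, and a general threshold of p < 0.05. It names no primary variable, does not refer back to the main criterion, and gives no order among the weight measures.

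**The concern.** The main question of the trial is answered from two weighings and a height. From those, the plan describes a continuous measure relative to excess weight, a continuous measure relative to total weight, and a yes/no threshold in kilograms. An analyst working from the design list and one working from the evaluation criteria would compute different quantities for what is meant to be the same comparison. Because the analysis section does not say which one decides, the choice could be made after the results are known.

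Two things are at stake. One is how far a free choice of measure loosens the 5% error rate. The other is that the stated 80% power belongs to a quantity that is not the main criterion.

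**Working it through.** **1. The plan's own figure.** Inputs from SAMPLE SIZE: 0.55 vs 0.39, α = 0.05, power 80%, loss 16%. Two-sided, pooled variance under the null, mean proportion 0.47:

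n per arm = [1.96·√(2·0.47·0.53) + 0.842·√(0.55·0.45 + 0.39·0.61)]² / 0.16² = (1.383 + 0.586)² / 0.0256 ≈ 152.

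After loss, 152/0.84 ≈ 181 per arm, 362 in total. One-sided gives 120 per arm, or 143 after loss. None of these gives 142 in total. That is a separate matter. What counts here is that the calculation concerns a ≥5 kg proportion, and no SD or mean difference for %EWL appears anywhere.

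**2. How the measures relate.** With baseline weight W, height h and loss L:

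- %TWL = 100·L/W
- %EWL = 100·L/(W − 25h²)
- so %EWL = %TWL × BMI/(BMI − 25)

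Eligibility is "BMI between 35 and 50 kg/m² and indication of one-time surgery", so the factor runs from 35/10 = 3.5, through 42.5/17.5 = 2.43, to 50/25 = 2.0.

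Patients can change order. A loss of 4% TWL at BMI 35 is 4 × 3.5 = 14% EWL, while 6% TWL at BMI 50 is 6 × 2.0 = 12% EWL.

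The 5 kg rule ignores body size. At an assumed height of 1.65 m, 5 kg is 5.25% TWL and 18.37% EWL at BMI 35 (95.3 kg), but 3.67% TWL and 7.35% EWL at BMI 50 (136.1 kg).

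**3. How often the choice changes the answer.** The documents give no distributions, so two sets of assumptions were simulated.

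- *Set A:* 60 per arm (71 × 0.84 = 59.6), BMI uniform on 35–50, mean %TWL 5, SD 3–5; height about 1.65 m (SD 0.09) where kilograms are needed.
- *Set B:* 71 or 60 per arm, BMI about 42.5 (SD 4) limited to 35–50, height about 1.65 m (SD 0.09), kilogram loss normal with SD 4 or 6, set so that 39% and 55% lose at least 5 kg.

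| Quantity | Set A | Set B |
|---|---|---|
| Correlation of %TWL and %EWL | about 0.95–0.97 | about 0.98 |
| %TWL and %EWL disagree on significance, true effect present | about 6–10% (0.25–0.5 SD) | about 6–8% |
| %TWL or %EWL disagrees with the ≥5 kg test, true effect present | – | about 24–25% |
| Null, two-sided: either of %TWL, %EWL at p < 0.05 | about 5.6–6.5% | – |
| Null, two-sided: any of the three at p < 0.05 | about 8.4–9.8% | about 8.5–8.7% |
| Null, result favouring the app: any of the three | about 4.2–4.7% | – |

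The last row compares with a nominal 2.5% in that direction.

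**4. What the planned size supports for %EWL.** For a two-sided t test with 80% power (normal approximation), the detectable standardised difference is (1.960 + 0.842)·√(2/n):

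- n = 71: 2.802 × 0.1678 = 0.47 SD
- n = 60: 2.802 × 0.1826 = 0.51 SD

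**The case against.** The strongest reply is that a primary measure is named. %EWL, with its reference BMI, is the only measure tied to the main goal, and the weighing times follow directly. The design list is unranked, mixes weight with satisfaction and morbidity, and labels nothing as primary. This stands. A reader might infer that the plan has two or three rival primary outcomes, or none; the documents do not support that.

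A reader might also infer that three tests of the main hypothesis are planned, each at 5%, with a false-positive rate near 9%. The ≥5 kg rate appears only as a sample-size assumption and is not a listed outcome. The p < 0.05 threshold is a general statement, not a rule that success on any measure counts. The roughly 9% applies only if an unlisted responder test is also allowed to decide. Even then it counts both directions, whereas the hypothesis is of greater loss with the app.

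Nor does the BMI-dependent factor bias the comparison. Randomised arms share the same expected BMI distribution, so it changes how patients are weighted and the precision, not the null.

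What the reply does not answer is that the design list gives a different measure for the same comparison, that the analysis section does not say which decides, and that the power statement concerns something else.

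**Conclusion.** The inconsistency is real and is in the current text, but it is moderate. The direct naming conflict is %TWL against %EWL. These usually agree, and choosing between them costs about one percentage point of two-sided error under the assumptions used. The larger practical gap is between the continuous measures and the ≥5 kg rate, and it bears mainly on the sample size: the stated 80% power cannot be carried over to %EWL.

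The algebra and the factors 3.5 and 2.0 follow from the documents. The error and disagreement rates rest on assumed SDs, BMI and height distributions and would shift with others.

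A reader might go further and conclude that the trial needs more patients for its main criterion. The documents give no %EWL difference or SD from which that could be shown. Severity: should-fix.

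**What to change.** Make three changes before any between-arm data are seen.

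1. **STUDY DESIGN:** replace the first item of the comparison list with %EWL (ideal BMI 25), from the weighing 4 months before surgery to the day of surgery.
2. **STATISTICAL ANALYSIS:** state that the main hypothesis is judged only on %EWL by the between-arm t test. Label %TWL, the ≥5 kg rate and the other weight measures as supportive.
3. **SAMPLE SIZE:** state that 142 patients and 80% power were planned on the ≥5 kg rate and do not apply to %EWL. Then give the precision or detectable difference for %EWL at the planned size: about 0.47 SD at 71 per arm, about 0.51 SD at 60 per arm after 16% loss, both at 80% power. A figure in %EWL units needs an SD that the sponsor would have to supply.

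The cost is an amendment to three sections. No new measurement is needed, because every measure uses the same two weights and height, and no extra patients are required. The sponsor gives up the freedom to claim success on another measure and must restate the power claim.
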